5.1.3 Quality Control

Monitoring

Before the first subject is recruited into the study, the local Marketing Company, MEOR Delivery Director, MEOR Operations Lead or CRO Representative will:

- Establish the adequacy of the facilities and the investigator's capability to appropriately select the sample
- Discuss with the investigator(s) (and other personnel involved with the study) their responsibilities with regards to protocol compliance, and the responsibilities of AstraZeneca or its representatives. This will be documented in an Observational Study Primary Agreement between AstraZeneca/delegate and the investigator.

During the study the local MC representative or delegate can implement different activities to assure compliance with AZ standards of quality. These activities could include but are not limited to:

Contacts with the sites to:

- Provide information and support to the investigator(s)
- Confirm that the research team is complying with the protocol and that data are being accurately recorded in the case report forms (CRFs)
- Ensure that the subject informed consent forms are signed and stored at the investigator's site
- Ensure that the CRFs are completed properly and with adequate quality.

Monitoring activities for:

- Checking of ICFs
- Checking that subjects exist in medical records

The extent and nature of monitoring will be decided during the study planning based on design, complexity, number of subjects, number of sites, etc. Observational Research Center (multi country) /Marketing Company (MC) will give some recommendations that could be locally adapted.

Different signals (eg, high rejection rate in a site) should be used as potential identification of low protocol compliance by investigators.

If these or any other signal occurs or if the local coordinator is suspicious of a potential non-optimal level of protocol compliance by the site investigator, specific measures should be adopted to evaluate the situation, identify the issue and implement specific action plans to correct the situation.

Training of Study Site Personnel

The Principal Investigator will ensure that appropriate training relevant to the Observational Study is given to investigational staff, and that any new information relevant to the performance of this Observational Study is forwarded to the staff involved.

5.2 Protection of Human Subjects

The Observational Study will be performed in accordance with ethical principles that are consistent with the Declaration of Helsinki, ICH GCPs, GPP and the applicable legislation on Non-Interventional Studies and/or Observational Studies.

The Investigator will perform the Observational Study in accordance with the regulations and guidelines governing medical practice and ethics in the country of the Observational Study and in accordance with currently acceptable techniques and know-how.

The final protocol of the Observational Study, including the final version of the Subject Informed Consent Form, must be approved or given a favourable opinion in writing by the Ethics Committee/Institutional Review Board (IRB)/Independent Ethics Committee (IEC). The Ethics Committee/IRB/IEC must also approve any amendment to the protocol and all advertising used to recruit subjects for the study, according to local regulations.

5.2.1 Subject Informed Consent (Primary Data Collection Only)

The Investigator will ensure that the subject is given full and adequate oral and written information about the nature, purpose, possible risk and benefit of the Observational Study. Subjects must also be notified that they are free to discontinue from the Observational Study at any time. The subjects should be given the opportunity to ask questions and allowed time to consider the information provided.

The signed and dated subject informed consent must be obtained before any specific procedure for the Observational Study is performed, including:

- Interview with the investigator
- Fulfil the questionnaires
- CRFs completion.

The Investigator must store the original, signed Subject Informed Consent Form. A copy of the signed Subject Informed Consent Form must be given to the subject.

5.2.2 Confidentiality of Study/Subject Data (Primary Data Collection Only)

The Subject Informed Consent Form will incorporate wording that complies with relevant data protection and privacy legislation. Pursuant to this wording, subjects will authorize the collection, use and disclosure of their personal data by the Investigator and by those persons who need that information for the purposes of the Observational Study.

The Subject Informed Consent Form will explain that Observational Study data will be stored in a computer database, maintaining confidentiality in accordance with the local law for Data Protection.

The Subject Informed Consent Form will also explain that for quality check purposes, a monitor of AZ or a monitor of company representing AZ, will require direct access to the signed subject informed consent forms. In case source data verification will be planned as quality check, the Subject Informed Consent Form will explain that for data verification purposes, monitor of AZ or a monitor of company representing AZ may require direct access to source documents that are part of the hospital or practice records relevant to the Observational Study.

5.3 Collection and Reporting of Adverse Events/Adverse Drug Reactions

5.3.1 Management of Adverse Risk

- a. Psychologic side-effects

Potential side effects include psychological distress due to issues raised regarding the potential presence of a hereditary cancer syndrome. It is possible that participants may experience anxiety as a result of the questionnaire process. Experience from our previous questionnaire protocols as well as clinical testing programs at the UCSD suggests that individuals do adjust to both information and the experience of participation in a predisposition testing program. There is variation in the degree to which participants rely on project staff for assistance. The program staff will be available throughout the program to respond to clinical questions and concerns that arise. Participants will also be offered the opportunity to receive psychological support from the center psychologist or social worker.

b. Privacy

There have been reports about the possibility of identifying an individual from his or her genetic information along with factors such as age and place of residence, even after the name has been removed. We believe that the chance of this happening in this study is very small but not zero, and will take measures to minimize such occurrences. Confidentiality will be assured by the coding of the questionnaires with a unique study ID assigned to each participant and family member. Files will be kept in password protected computer databases accessible to only study staff. The listing of participant names and numbers will be kept in a separate locked file within the Clinical Trials Office. It will be recommended to participants that they inform their physician of their test results.

c. Insurance Discrimination

The study itself is testing and educational intervention and genetic testing will be performed as standard of care should a participant decide to pursue genetic testing. The Genetic Information Nondiscrimination Act of 2008 (GINA) protects Americans from being treated unfairly because of differences in their DNA that may affect their health, and may prevent discrimination by health insurers and employers based on genetic information. GINA is intended to ease concerns about discrimination that might keep some people from getting genetic tests that could benefit their health, and enable people to take part in research studies such as this without fear that their DNA information might be used against them by health insurers or their workplace. This protection does not extend to disability or life insurance. A current or prior cancer diagnosis is likely to be the most significant factor affecting life insurance, or rates and eligibility for other forms of insurance. Genetic testing information is unlikely to change this risk.

5.3.2 Definition of Adverse Events (AE)

An AE is any untoward medical occurrence in a patient or clinical study subject administered a medicinal product and which does not necessarily have a causal relationship with this treatment. An adverse event can therefore be any unfavourable and unintended sign (e.g. an abnormal laboratory finding), symptom, or disease temporally associated with the use of a medicinal product, whether or not considered related to the medicinal product.

The term AE is used to include both serious and non-serious AEs.

5.3.3 Definition of Serious Adverse Events (SAE)

A serious adverse event is an AE occurring during any study phase (i.e., run-in, treatment, washout, follow-up), that fulfils one or more of the following criteria:

- Results in death

- Is life-threatening (life-threatening in this context refers to a reaction in which the patient was at risk of death at the time of the reaction; it does not refer to a reaction that hypothetically might have caused death if more severe)
- Requires in-patient hospitalisation or prolongation of existing hospitalisation
- Results in persistent or significant disability or incapacity
- Is a congenital abnormality/birth defect
- Is an important medical event that may jeopardise the subject or may require intervention to prevent one of the outcomes listed above. Medical and scientific judgement should be exercised in deciding whether other situations should be considered an SAE.

Any suspected transmission via a medicinal product of an infectious agent is also considered an SAE and may be subject to expedited reporting requirements in some countries. Any organism, virus or infectious particle (for example Prion Protein Transmitting Transmissible Spongiform Encephalopathy), pathogenic or non-pathogenic, is considered an infectious agent.

It is important to distinguish between serious and severe AEs. Severity is a measure of intensity whereas seriousness is defined by the criteria in Sections 6.3.2. An AE of severe intensity need not necessarily be considered serious. For example, nausea that persists for several hours may be considered severe nausea, but not a SAE unless it meets one of the criteria shown in Section 6.3.2. On the other hand, a stroke that results in only a limited degree of disability may be considered a mild stroke but would be a SAE if it satisfies one of the criteria shown in Section 6.3.2.

6. APPENDICES

Appendix A: Patient Survey on Germline Testing in Prostate Cancer

Participant Name: _____

Participant Study ID: _____

Date: _____

The purpose of this section is to understand what you know generally about inherited cancer risk (genetic risk that occurs within a family). By understanding what you may or may not know about inherited cancer risk it may help us to improve our educational sessions.

Below we have listed some general questions about genetics and multi-gene panel testing (a genetic test that evaluates more than one gene). These questions are not specific to you or your risk but rather common questions about genetic risk.

Section A:

Please answer these questions as True or False.

		True	False
1.	Genes are made from pieces of DNA		
2.	A mutation is a change in DNA sequence		
3.	Cancer is caused by a combination of inheritance, environmental exposure, and lifestyle factors		
4.	Most people who develop cancer do so because they have inherited risk for cancer that they were born with.		
5.	All of the gene mutations that could increase risk for cancer have been discovered.		

Section B

Please answer these questions with agree, disagree, or if you are unsure, "I don't know".

		Agree	Disagree	I don't know
1.	My doctor has talked to me about genetic testing for my prostate cancer prior to enrolling in this study.			
2.	Some men with prostate cancer were born with genetic mutations which contributed to their development of cancer.			

3.	Knowing about inherited risk (passed down within a family) can affect choices about cancer treatments (for example, medications or surgery).			
4.	People with an inherited risk for cancer (and their at-risk relatives) are more likely to develop more than one type of cancer.			
5.	The blood relatives (for example, sister, father, or child) of a person with a mutation in a cancer risk gene might share the same gene mutation.			
6.	A person with an inherited risk for cancer may have distant relatives (for example, cousins) who also have increased cancer risk.			
7.	All children of a person with inherited cancer risk will also have inherited cancer risk.			

Section C

The following questions are about the extent of your interest in genetic testing for your cancer.

- How interested are you in undergoing genetic testing to determine if you were born with any genetic mutations which predisposed you to developing prostate cancer?
 - Very interested
 - Interested
 - Neutral
 - Not interested
 - Not at all interested
- Of the following listed factors, which would **most** influence you in a decision to pursue germline DNA testing in the care of your cancer? (**Rank answers in orders of preference from 1 to 5, 1= best describes, 5= least describes**)

	Rank (1 = best, 5 = least)
Potential to guide treatment selection	
Potential to predict disease outcome	
Potential to learn more about my cancer risk	
Potential to learn more about the cancer risk of my family	
Trust in my physician and their recommendation for genetic testing	
Other (please specify; not required)	

3. Of the following listed factors, which would **most** influence you in a decision to **not** pursue genetic DNA testing in the care of your cancer? (**Rank answers in orders of preference from 1 to 5, 1= best describes, 5= least describes**)

	Rank (1 = best, 5 = worst)
Potential of DNA test results to be of no clinical value	
Potential of DNA test results to lead to health, life or disability insurance discrimination	
Concerns about the privacy and confidentiality of DNA test results	
Concerns about the impact a positive result would have on my family and relatives.	
Other (please specify; not required)	

4. At the start of this educational session, my current decision on pursuing genetic testing is:

- A) I want to proceed with germline testing done today.
- B) I do not want to proceed with germline testing today.
- C) I am unsure at this time.

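### Survey item C3 (reasons not to test) labels rank 5 in two different ways and asks for five ranks over four named rows, so barrier ranks may be blurred and are not fully comparable between men

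*Combined protocol and SAP*

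**What the plan says.** **The item.** In Appendix A, Section C, item 3 asks what would most influence a man not to pursue testing. Its instruction is "Rank answers in orders of preference from 1 to 5, 1= best describes, 5= least describes". The column he fills in is headed "Rank (1 = best, 5 = worst".

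**Its sister item.** Item 2, on reasons to pursue testing, has the same instruction, but its column is headed "Rank (1 = best, 5 = least".

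**The rows.** Item 3 names four factors: a result without clinical use, discrimination by insurers, loss of privacy, and the effect of a positive finding on the family. A fifth row, 'Other', is marked as optional. Item 2 names five factors and adds an optional 'Other'.

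**Where it is used.** The post-session survey in Appendix C repeats item 3 with the same instruction, header and rows. Section 5.1.2 says that 14 knowledge and attitude items are common to both surveys. Section 4.2 makes patient opinions before and after the session part of secondary endpoint 2. Section 4.5.2 plans descriptive summaries only, among them percentages, means and standard deviations. No section gives a rule for coding or checking the ranks.

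**The concern.** The rows of C3 are worries. Beside a list of worries, 'worst' has two possible senses: the row that fits worst, which agrees with the instruction, or the worst of the worries, which is its opposite. A man who takes the second sense gives 5 to his main barrier, where the instruction calls for 1. If some men do this, the item mixes two scale directions.

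The rank count is a separate defect. Five ranks are requested for four rows that must be filled. A man who leaves 'Other' blank has to decide which rank to leave out, and nothing tells him which.

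At stake is the description of what deters men from testing. C3 is the only structured patient item on that question, so other answers cannot stand in for it. Both defects appear in both surveys.

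**Working it through.** The plan states no figure for this item, so there is none to reproduce. The check compares the texts, counts rows against ranks, and then works out what a mixed scale direction would do.

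**1. Labels and rows side by side** (Appendix A, Section C; the same in Appendix C)

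| | Item 2 (reasons to test) | Item 3 (reasons not to test) |
|---|---|---|
| Rank 5 in the instruction | least | least |
| Rank 5 in the column header | least | worst |
| Named rows | 5 | 4 |
| Optional 'Other' | yes | yes |
| Ranks requested | 1 to 5 | 1 to 5 |

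Item 2 agrees with itself on both counts. Item 3 does so on neither. The 'worst' header occurs in both appendices, so it is not an accident of text extraction.

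**2. Does C3 feed the before-and-after endpoint?** Appendix C repeats 5 items in Section A, 6 in Section B and 3 in Section C: 5 + 6 + 3 = 14. This matches the 14 common items in section 5.1.2, so C3 is one of them.

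**3. Rank count, with 'Other' blank and distinct ranks used.**
- Ways to place 5 distinct ranks on 4 rows: 5 × 4 × 3 × 2 = 120.
- Ways with no rank 1 (only 2 to 5 used): 4! = 24.
- Ways with no rank 5 (only 1 to 4 used): 4! = 24.
- Orderings of four concerns: 4! = 24, so each ordering can be written in 120 / 24 = 5 ways.

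Two men with the same order of concerns can therefore record different numbers. One might write 1, 2, 3, 4 and another 2, 3, 4, 5. A man who does rank 'Other' adds a further pattern. With ranks 1 to 4 over four rows, only 24 rankings exist, and each has exactly one rank 1 and one rank 4. These are counts of possible forms, not forecasts of how often each would occur.

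**4. Reversed reading.** Let p be the share of men who reverse the scale, the same whatever their true ranking. The documents give no value for p. For a factor with true mean rank m on five ranks:

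recorded mean = (1 − p)m + p(6 − m) = 3 + (1 − 2p)(m − 3)

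Every factor's distance from the mid-rank is multiplied by (1 − 2p). For p below 0.5 this multiplier is positive, so the expected order of the mean ranks is kept and only the gaps shrink. At p = 0.5 all the means meet at 3.

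As an illustration only, a factor that every man truly ranks first has recorded mean 1 + 4p:

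| Assumed p | 5% | 10% | 20% | 30% |
|---|---|---|---|---|
| Recorded mean rank (true value 1) | 1.2 | 1.4 | 1.8 | 2.2 |

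The order-keeping result is for mean ranks. The recorded share ranking a factor first becomes a mix of its true 'first' and true 'last' shares. It is blurred too, but does not carry the same guarantee.

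**The case against.** The best reply is that the two labels need not conflict. The instruction is explicit, the header itself calls 1 'best', and item 2, just above, runs the same way. Beside 'best', the simplest sense of 'worst' is worst-fitting. This stands: reversal is a possible reading, not the evident one.

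Four stronger inferences are tempting, and the documents support none of them.

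- *The main barrier will be recorded backwards.* This would need a majority of men to misread, or misreading that depends on a man's own concerns. Neither is shown. The rank-count mismatch reverses nothing by itself.
- *A completed form can never show how it was read.* That is too absolute. A form with a 5 and no 1 hints at reversal, though it does not prove it, since the rank count allows such a form under either reading. The session outline in section 3.1 includes both surveys, and section 5.1.2 allows completion by phone with staff, so clarification is often at hand. It is less so for surveys completed through an emailed link.
- *A man who reads the header differently the second time will be counted as a session effect.* This is arithmetically possible, but no figure on switching is given and section 4.5.2 describes no analysis of individual rank changes.
- *The insurance row should be split, because section 5.3.1 says of the federal law* "This protection does not extend to disability or life insurance". Keeping three kinds of insurance in one row is a design preference, not a contradiction. Whether the session would move these worries apart depends on a brochure that is not reproduced.

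It is also fair to say that the stakes are modest. No hypothesis concerns barrier ranks, and the interest item and the decision item bear more directly on the attitude hypothesis.

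**Conclusion.** The concern holds as a flaw in a data-collection form. C3 gives rank 5 two different labels, so some men could rank in reverse. It also requests one rank more than it has named rows, so ranks are not fully comparable between men. Both faults are plain on the page, in both appendices.

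The effect is limited to one item within a descriptive secondary endpoint. The primary endpoints and the target of 50 patients are untouched. The size of the reversal effect is unknown, because it depends wholly on a misreading rate that the documents do not give. If that rate is common to all men and below 50%, the expected mean ranks are pulled together but keep their order. The rank-count result assumes that 'Other' is left blank and that no rank is used twice.

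**What to change.** In Appendices A and C and in the matching REDCap fields:

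1. Use one anchor pair in both the C3 instruction and the column header, for example '1 = most influences me not to test, 4 = least'.
2. Rank only the four named rows, 1 to 4.
3. Make 'Other' unranked free text.
4. State in section 4.5.2 that C3 is summarised as the percentage ranking each factor first.

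The insurance row can stay as it is.

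The cost is a wording edit on two investigator-developed forms. The milestones place the final survey instruments in July 2021 and the start of accrual in October 2021, and this version is dated 12/06/2021, so forms with the old header may already be in use. If so, identify them and show C3 with and without them. The small downside is that old and new forms are not fully poolable for this item.

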Appendix B: Family History Questionnaire

Patient Name:

Medical Record #

Family History Questionnaire

Part 1: Personal history information

Have you had any genetic testing of your **tumor** tissue? Yes No Not sure
(examples: Foundation, Guardant, Tempus, or Caris testing)

Health history/ancestry:

Ancestry (e.g. Swedish, Japanese, English)

Mother's side:

Father's side:

Any Ashkenazi Jewish Ancestry? Yes No What side of the family?

Ever had a colonoscopy? Yes No If yes, any history of colon polyps?

Other health issues you'd like to share

Have you had genetic counseling because of your family history of cancer before? Yes No
Not sure

If so, where was the genetics consultation done? UCSD Elsewhere:

Genetic Testing History

Have you ever had genetic testing for cancer risk before?

Yes No Not Sure

Observational Study Protocol Form

Version 3.0

Form Doc ID: AZDoc0059948

Parent Doc ID: SOP LDMS_001_00164328

If yes, please describe (what test, what year completed if known)

What were the results?

gene

A mutation was found in the

(Important: Please bring copies of results)

gene

No mutations were found

My results were "uncertain" in the

I'm not sure

Please describe any other genetic testing findings or issues:

Yes No Not Sure

If yes, please describe which relative(s) and their results, if known (**Important: If possible, please bring copies of reports**)

Part 2. Your children:

How many children (living and deceased)? _____

Please list your sons and daughters on the rows below (if you need more rows, please use the back of this form):

Relative	Ever diagnosed with cancer?	Check if deceased	Current age/ Age at death	Cancer Type	Age at diagnosis
Son  Daughter 	Y  N 				
Son  Daughter 	Y  N 				
Son  Daughter 	Y  N 				

Son 	Daughter 	Y 	N 				
Son 	Daughter 	Y 	N 				
Son 	Daughter 	Y 	N 				

Part 3. Your brothers and sisters:

How many brothers and sisters (living and deceased)? _____

Please list your brothers and sisters on the rows below (if you need more rows, please use the back of

Relative	Ever diagnosed with cancer?	Check if deceased	Current age/ Age at death	Cancer Type	Age at diagnosis
Brother 	Sister 	Y 	N 		
Brother 	Sister 	Y 	N 		
Brother 	Sister 	Y 	N 		
Brother 	Sister 	Y 	N 		
Brother 	Sister 	Y 	N 		
Brother 	Sister 	Y 	N 		
Brother 	Sister 	Y 	N 		

(this form)

Part 4. Your mother's side of the family:

Relative	Ever diagnosed with cancer?	Check if deceased	Current age or Age at death	Cancer Type	Age at diagnosis

Mother	Y  N 				
Maternal grandmother	Y  N 				
Maternal Grandfather	Y  N 				

How many aunts and uncles (living and deceased) on your **mother's side**? _____

Please list **all** of your aunts and uncles (**mother's side**) on the rows below (if you need more rows, please use the back of this form):

Relative	Ever diagnosed with cancer?	Check if deceased	Current age/ Age at death	Cancer Type	Age at diagnosis
Aunt  Uncle 	Y  N 				
Aunt  Uncle 	Y  N 				
Aunt  Uncle 	Y  N 				
Aunt  Uncle 	Y  N 				
Aunt  Uncle 	Y  N 				
Aunt  Uncle 	Y  N 				

Part 5. Your father's side of the family:

Relative	Ever diagnosed with cancer?	Check if deceased	Current age or Age at death	Cancer Type	Age at diagnosis
Father	Y  N 				

Paternal grandmother	Y  N 				
Paternal Grandfather	Y  N 				

How many aunts and uncles (living and deceased) on your **father's side**? _____

Please list your aunts and uncles (**father's side**) on the rows below (if you need more rows, please use the back of this form):

Relative	Ever diagnosed with cancer?	Check if deceased	Current age/ Age at death	Cancer Type	Age at diagnosis
Aunt  Uncle 	Y  N 				
Aunt  Uncle 	Y  N 				
Aunt  Uncle 	Y  N 				
Aunt  Uncle 	Y  N 				
Aunt  Uncle 	Y  N 				
Aunt  Uncle 	Y  N 				
Aunt  Uncle 	Y  N 				
Aunt  Uncle 	Y  N 				

